3.3 Sample Size Justification

The sample size is driven by interest in the IOP lowering effect of H-1337. The study is designed to test whether one or more concentrations of H-1337 are non-inferior to the timolol control in the reduction of IOP. As benefit is represented by a negative number, non-inferiority is achieved when the upper limit of the confidence interval of the difference in treatment (H-1337 minus Timolol) is strictly lower than the non-inferiority margin.

A sample size of 45 subjects per group will allow for at least 90% power to establish non-inferiority of H-1337 over Timolol based on a non-inferiority limit of 2 mmHg, a standard deviation of 3.0 mmHg and a 1-sided t-test (alpha=0.05).

Assuming that 10% of the subjects will not be eligible in the Intent-to-Treat (ITT) population, a total of 50 subjects per group is required.

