4.1 Definitions and Conventions

Listings present the subjects individual data, while summary tables present the summary statistics of subjects data.

Summary statistics will be presented for continuous variables, by way of n, mean, standard deviation (SD), median, minimum and maximum. For categorical variables including binary variables, frequency counts and percentages will be presented. Percentages will be calculated using the total number of subjects per treatment groups or the total number of subjects with an assessment per treatment groups, depending on the nature of the analysis.

In addition, 95% 2-sided confidence intervals (CIs) will be presented, where relevant. In case of percentages, the CI will be computed using the Clopper-Pearson method. The CI will be computed for continuous variables using a t-test analysis.

Summary statistics will be displayed by treatment groups, which will be labelled as follow:

- Group 1: H-1337 0.6%
- Group 2: H-1337 1.0% b.i.d
- Group 3: H-1337 1.0% q.a.m
- Group 4: Timolol 0.5%

Baseline Value is defined as the last non-missing value prior to the first IP administration for vital signs, BCVA, biomicroscopy and dilated ophthalmoscopy (Day 1 Pre- T_0 for vital signs, BCVA and biomicroscopy; Screening for dilated ophthalmoscopy). For IOP and conjunctival hyperemia grading, time-matched baseline values are defined at Pre- T_0 on Day 1 (Visit 3), T_0 +2 hours, T_0 +4 hours, T_0 +8 hours and T_0 +12 hours on Day 0 (Visit 2). For mean diurnal IOP, baseline is defined at Day 0.

Change from Baseline is defined as the difference in value of the assessment between the considered visit and the baseline value. In the case of IOP and conjunctival hyperemia grading, change from Baseline is the difference in value of the assessment between the considered visit at a particular timepoint and the corresponding baseline value.

Study eye is defined as the eye that meets all entry criteria including the IOP criteria after washout. Should both eyes meet the criteria then the study eye will be the eye with the higher 8 am IOP at Baseline (Day 1). If both eyes have the same 8 am IOP at Baseline (Day 1), the study eye will be the right eye.

SAS® version 9.4 or above will be used to perform the analyses.

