4.11.1 Primary Efficacy Analyses

Change from Baseline in IOP (mmHg) at Day 28 and Day 1 (on-treatment time points) in the study eye is the primary efficacy endpoint. It will be summarized by timepoint and treatment group in the ITT population primarily and in the PP population secondarily. The endpoints will be analysed using an analysis of covariance (ANCOVA) model including baseline value and treatment groups as independent variables. The least square (LS) means, standard error (SE) and 2-sided 95% CI will be reported for each treatment group at each post-randomization visit.

In addition, the differences between treatments (H-1337 vs Timolol) will be calculated for each H-1337 treatment group. A time-matched longitudinal model adjusting for baseline and including a random effect for subject will be used to calculate the LS mean, SE, and 2-sided 95% CI for the between-treatments differences. The model will also be tested for treatment by visit and treatment by time points interactions. If no interactions are detected, the main effect model will be used. The variance-covariance matrix-structure used in the model will be the unstructured (TYPE=UN). If convergence is not achieved, a compound-symmetry structure will be used (TYPE=CS).

The testing procedure for non-inferiority will be performed as described in Section 4.3.

Missing values will not be imputed.

All summaries generated for IOP will be using the mean/median value recorded in the case report form.

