4.11.2 Secondary Efficacy Analyses

The secondary efficacy endpoints are all related to IOP in the study eye.

Change from Baseline in IOP at Day 7 and Day 14 in the study eye will be summarised by visit, timepoint and treatment group. The endpoints will be analyzed using an ANCOVA model including baseline value and treatment groups as independent variables. The LS means, SE and 2-sided 95% CI will be reported for each treatment group at each post-randomization visit.

In addition, the differences between treatments (H-1337 vs Timolol) will be calculated and summarised by visit, timepoint and treatment group (for each of the H-1337 groups). The ANCOVA model will be used to calculate the LS mean, SE, and, 2-sided 95% CI for the between-treatments differences.

Similar analyses will be performed for the following endpoints:

- IOP.
- percentage change from Baseline in IOP,
- mean diurnal IOP (12-hour diurnal),
- change from Baseline in mean diurnal IOP (12-hour diurnal),
- percentage change from Baseline in mean diurnal IOP (12-hour diurnal),
- mean diurnal IOP (8-hour diurnal),
- change from Baseline in mean diurnal IOP (8-hour diurnal),
- percentage change from Baseline in mean diurnal IOP (8-hour diurnal).

Where multiple IOP assessments are made on the same day, mean diurnal IOP (12-hour diurnal) is defined as the average of all multiple assessments (Pre T_0 is excluded from the calculation). Mean diurnal IOP (8-hour diurnal) is defined as the average of all assessments up to 04:00pm (Pre T_0 is excluded from the calculation). The visit at which a subject is missing more than (>) 2 assessments for the calculation of mean diurnal IOP will be excluded from the analysis in the PP population.

The number and percentage of subjects with IOP ≤18 mmHg will be summarized by visit, timepoint and treatment group. The 2-sided 95% CI will be calculated using the Clopper-Pearson method. In addition, the difference in proportions between treatments (H-1337 vs Timolol) will be calculated and summarised by visit, timepoint and treatment group (for each of the H-1337 groups). The 2-sided 95% CI for the difference in proportions will be computed using the Wald method.

A similar analysis will be performed for the following 2 endpoints:

- number and percentage of subjects with mean diurnal IOP (12-hour diurnal) ≤18 mmHg, and
- number and percentage of subjects with mean diurnal IOP (8-hour diurnal) ≤18 mmHg.

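### The IOP ≤18 mmHg responder differences are not adjusted for baseline IOP, which gives up some precision on a secondary endpoint

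*SAP*

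**What the plan says.** SAP 4.11.2 tabulates the proportion of subjects at or below 18 mmHg in the study eye, with Clopper-Pearson intervals. For the comparison with timolol, "the difference in proportions between treatments (H-1337 vs Timolol) will be calculated and summarised by visit, timepoint and treatment group". The interval is specified as follows: "The 2-sided 95% CI for the difference in proportions will be computed using the Wald method". The same treatment is given to the 8-hour and 12-hour mean diurnal responders. No covariate, stratification factor or model is named. SAP 4.11.3 repeats all IOP analyses in the fellow eye.

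The continuous IOP comparisons are handled differently:

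- The primary treatment differences (SAP 4.11.1) come from this model: "A time-matched longitudinal model adjusting for baseline and including a random effect for subject".
- The secondary ANCOVA (SAP 4.11.2) is specified as "including baseline value and treatment groups as independent variables", and "The ANCOVA model will be used to calculate the LS mean, SE, and, 2-sided 95% CI for the between-treatments differences". It is extended by analogy to observed IOP, percentage change and mean diurnal IOP.

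The covariate already exists. SAP 4.1 states: "For IOP and conjunctival hyperemia grading, time-matched baseline values are defined at" Pre-T0 on Day 1 and the +2, +4, +8 and +12 hour readings on Day 0. Day 0 is also the baseline for mean diurnal IOP.

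**The concern.** The cut-off is absolute, so where an eye starts affects whether it gets there. At the 8 am Day 1 entry limits (protocol 4.1), a study eye at 23 mmHg needs a fall of 5 mmHg to reach 18, and one at 32 mmHg needs a fall of 14. Neither document describes stratifying randomization by baseline IOP. Variation in the responder outcome that baseline could explain therefore stays in the standard error of the crude difference.

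What is at stake is the width of the responder intervals in a four-arm study with about 50 subjects per arm. A lesser point is ease of reading: a chance baseline difference is adjusted out of the mean analysis at a given time point but not out of the responder analysis beside it. No test, margin or decision rule is attached to this endpoint, and it is not in the sequence in SAP 4.3.

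**Working it through.** **1. The plan's own figure.** SAP 3.3 says "A sample size of 45 subjects per group will allow for at least 90% power", "based on a non-inferiority limit of 2 mmHg", with SD 3.0 and one-sided alpha 0.05. Taking the true difference as zero (not stated), the standard error is 3 × √(2/45) = 0.632 and 2/0.632 = 3.16. Power is Φ(3.16 − 1.645) = 93.5%, or 93.2% with the t distribution, so the statement holds. Then 45/0.90 = 50 per group. This sizing concerns mean IOP. The documents give no precision or power figure for the responder endpoint.

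**2. Inputs the documents do not give.** Responder rate: assumed 20–60% in the table inputs and main simulation, and 15–50% in the second simulation. Correlation of baseline with on-treatment IOP: assumed 0 to 0.7.

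**3. Crude interval.** With responder rate p in both arms and n per arm, the Wald half-width is 1.96 × √(2p(1 − p)/n). For p = 0.40 and n = 50 this is 1.96 × √0.0096 = 1.96 × 0.098 = 19.2 percentage points.

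**4. What adjustment removes.** If the responder outcome is a normal variable cut at a threshold and has correlation ρ with baseline, the share of its variance explained by baseline is R² = [ρ φ(z_p)]² / [p(1 − p)]. The half-width is multiplied by √(1 − R²), and the gain in effective sample size is R²/(1 − R²). For p = 0.40, φ(z_p) = 0.386. At ρ = 0.5, R² = (0.5 × 0.386)²/0.24 = 0.155, and the half-width becomes 19.2 × √0.845 = 17.7 points.

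| ρ | R² (p = 0.40) | half-width, n = 50 | gain in effective n |
|---|---|---|---|
| 0.3 | 0.056 | ±18.7 | 6% |
| 0.5 | 0.155 | ±17.7 | 18% |
| 0.7 | 0.305 | ±16.0 | 44% |

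At ρ = 0.5, R² runs from about 0.11 (15% responders) to 0.16 (50% responders).

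**5. Simulation with the entry range imposed.** There were 4,000 trials per setting with 45 or 50 per arm. Responder rates were 40% v 40%, 30% v 50% and 20% v 20%. Baseline was normal with mean 24 and SD 3 (assumed), truncated to 23–32 mmHg, and ρ was the correlation within the truncated population. The adjusted estimate was a logistic model on treatment and baseline, standardised to a marginal risk difference. The standard error fell by 1.4–2.7% at ρ = 0.3, 4.1–7.8% at 0.5 and 9.4–16.3% at 0.7. At ρ = 0 it rose by less than 1%. Both estimators target the same quantity: with 45 per arm, rates of 30% v 50% and ρ = 0.3, the mean estimates were −0.200 crude and −0.199 adjusted. With 50 per arm and ρ = 0.5, the effective sample size gain was 10% at 20% responders and 18% at 40%, that is 0.10 × 50 = 5 to 0.18 × 50 = 9 subjects per arm.

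**6. If the correlation is the one before entry restriction.** Take baseline as normal with mean 25 and SD 2.5 (assumed) before truncation to 23–32. Truncation leaves 0.548 of the variance, so ρ = 0.5 becomes √[0.25 × 0.548/(0.25 × 0.548 + 0.75)] = 0.39 within the trial. A simulation on this basis, with 15–50% responders, gave variance reductions of about 1–2% at 0.3, 2–5% at 0.4, 4–10% at 0.5 and 5–15% at 0.6. At 0.5 that is 50 × 0.04/0.96 = 2 to 50 × 0.10/0.90 = 5 or 6 subjects per arm.

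**7. Chance imbalance.** A baseline imbalance of one standard error, √(2/50) = 0.2 SD, shifts the crude difference by ρ φ(z_p) × 0.2 = 0.5 × 0.386 × 0.2 = 3.9 points at p = 0.40 and ρ = 0.5. Its squared size, 0.0386² = 0.00149, divided by the crude variance 0.0096 is 0.155, which is R² again. The Wald variance therefore already contains this component.

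**The case against.** The strongest case is that this is a preference for efficiency and not a fault. The crude risk difference is unbiased under randomization, reads directly as the stated endpoint, and carries no formal inference. That stands in full.

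A reader might infer that chance baseline imbalance makes the responder comparison biased or its interval wrong. The documents do not support that. Step 7 shows that the imbalance is already counted in the crude variance, so the cost is width. Type I error and the primary conclusion are untouched. Nor would adjustment guarantee agreement with the mean analysis: a dichotomised outcome and a mean can differ after adjustment too.

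A reader might also look for one firm figure for the gain. None is available. The correlation is undocumented, the entry limits can lower it at 8 am, and the +2 to +12 hour baselines come from a different day, Day 0, up to four days before dosing. On the other side, the 23 mmHg floor applies only at the 8 am Day 1 reading and only in the study eye, so the restriction is weaker elsewhere.

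It would also be too broad to say that all continuous IOP results are adjusted. SAP 4.1 provides unadjusted t-based intervals for descriptive summaries. The contrast holds for between-treatment analyses.

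Finally, the adjusted model needs the time-matched baseline and the crude one does not. With no imputation (SAP 4.2), some subjects could drop out, offsetting part of a small gain. Sparse responder counts also need a fallback. Both points stand and are met in the fix.

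**Conclusion.** The point holds as one of precision. The responder differences ignore a covariate that the trial collects and uses for the between-treatment analyses of continuous IOP. Under the assumed responder rates, and with the correlation taken within the trial population, the standard error would fall by roughly 1–3% at 0.3, 4–8% at 0.5 and 9–16% at 0.7, with a loss below 1% at zero. At 0.5 the gain equals about 2 to 9 subjects per arm of 50. Where it falls in that range depends on the responder rate and on whether the correlation is taken before or after the entry restriction. This is a worthwhile, low-priority improvement to a secondary endpoint.

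**What to change.** In SAP 4.11.2:

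- Estimate each responder difference from a logistic model with treatment and the time-matched baseline IOP. For the diurnal responders use the corresponding Day 0 mean diurnal IOP.
- Standardise over all analysed subjects to a marginal risk difference, and name the 95% interval method (delta method or bootstrap). A conditional odds ratio would change the estimand and should not replace the difference.
- Keep the raw proportions with Clopper-Pearson intervals, and the crude difference, as description.
- Before unmasking, fix a numeric minimum of responders and non-responders below which only the unadjusted difference is reported, so that the switch does not depend on the results.
- State how subjects without the time-matched baseline are handled.
- Apply the same rule, with the fellow eye's own baseline, to the repeat analysis in SAP 4.11.3.

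The cost is a few lines of SAP text and code. No new data are needed and the testing sequence does not change. SAP section 1 allows amendment before database lock. The downsides are small: a fallback rule is needed, one table may mix adjusted and unadjusted entries, and subjects without a baseline may be lost from the adjusted estimate.

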3. STUDY DESIGN

3.1 Study Design

The trial will evaluate the safety and efficacy of 3 dose regimens of H-1337 (0.6% b.i.d., 1.0% b.i.d. and 1.0% q.a.m., and timolol maleate (0.5%, b.i.d.) OU for 28 days (\pm 2-day allowable window for Day 28).

Approximately 200 subjects will be randomized and dosed for 28 days. The parallel group, double-masked, active-controlled study will include the following dosing cohorts:

- H-1337 0.6% Ophthalmic Solution b.i.d. (n=50)
- H-1337 1.0% Ophthalmic Solution b.i.d. (n=50)
- H-1337 1.0% Ophthalmic Solution q.a.m. and H-1337 placebo q.p.m. (n=50)
- Timolol 0.5% Ophthalmic Solution b.i.d (n=50)

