4.11 Efficacy Analyses

All efficacy analyses will be performed using both the ITT and PP populations. Missing values will not be imputed.

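### The Wald interval for the difference in responder proportions under-covers when rates are unequal and one is below about 5%, and has zero width when neither arm has a responder; a score interval is a near-free replacement

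*SAP*

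**What the plan says.** SAP 4.11.2 defines the responder summary: "The number and percentage of subjects with IOP ≤18 mmHg will be summarized by visit, timepoint and treatment group". For each arm's own proportion it uses an exact method: "The 2-sided 95% CI will be calculated using the Clopper-Pearson method". For the H-1337 minus timolol difference it changes method: "The 2-sided 95% CI for the difference in proportions will be computed using the Wald method". The same treatment applies to the 12-hour and 8-hour mean diurnal versions. SAP 4.11 runs all efficacy analyses in both the ITT and PP populations, and SAP 4.11.3 repeats the IOP analyses in the fellow eye. No fallback is given for sparse or empty cells.

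On size, SAP 3.3 says "A sample size of 45 subjects per group will allow for at least 90% power" and then "Assuming that 10% of the subjects will not be eligible in the Intent-to-Treat (ITT) population, a total of 50 subjects per group is required". On missing data, SAP 4.11 says "Missing values will not be imputed". The schedule tables in both documents (Protocol Table 1 and SAP Appendix 1, footnote 3) make the T0+12 hour assessment optional for new subjects under protocol version 3.0.

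Neither document states an expected responder rate or a target precision for this difference.

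**The concern.** The Wald interval estimates its standard error from the observed proportions. When an observed proportion is 0 that arm contributes no variance, and when both are 0 the interval has no width. The contrast between arms, which is what a reader will use to compare H-1337 with timolol, therefore gets a weaker method than the single-arm proportions printed beside it.

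At stake is the reading of a named secondary endpoint, shown for three contrasts over many visits and time points. In a sparse cell with unequal rates, an interval labelled 95% may exclude differences that the data cannot exclude. A table could also show [0, 0] for a difference while each arm's exact interval runs from 0 to about 7%.

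**Working it through.** **Inputs.** n = 50 per arm (Protocol 3.1, SAP 3.3), or 45 after the 10% allowance; equal allocation; 2-sided 95%. Responder rates are not in the documents, so a range is used.

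**The plan's own figure.** Margin 2 mmHg, SD 3.0 mmHg, 1-sided alpha 0.05, and a true difference of 0 (assumed; not stated). Normal approximation: n = 2 × 9 × (1.645 + 1.282)² / 4 = 38.5, so 39 per arm. At n = 45, 2 / (3 × √(2/45)) = 3.162, and 3.162 − 1.645 = 1.517, giving 93.5% power (93.2% by the t-test). The claim of at least 90% holds, and 45 / 0.9 = 50.

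**Formulas.** With observed proportions a and c, the Wald interval is a − c ± 1.96 × √[a(1−a)/n + c(1−c)/n]. Exact coverage is the sum, over all pairs of counts (x, y), of the two binomial probabilities for pairs whose interval contains p1 − p2.

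**Coverage (%), by full enumeration:**

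| True rates | Wald n=45 | Wald n=50 | Newcombe n=45 | Newcombe n=50 | Miettinen-Nurminen n=45 | Miettinen-Nurminen n=50 |
|---|---|---|---|---|---|---|
| 2 v 2 | 99.0 | 98.7 | 99.8 | 99.8 | 99.0 | 98.7 |
| 2 v 5 | 88.7 | 91.4 | 99.1 | 98.9 | 98.3 | 97.8 |
| 2 v 10 | 92.6 | 93.3 | 97.4 | 97.5 | 94.8 | 93.7 |
| 5 v 5 | 95.1 | 94.6 | 98.2 | 97.9 | 95.9 | 95.7 |
| 5 v 10 | 94.9 | 94.7 | 97.1 | 96.9 | 95.8 | 94.7 |
| 10 v 20 | 94.7 | 94.6 | 95.6 | 95.7 | 95.3 | 95.0 |
| 20 v 30 | 94.5 | 94.4 | 95.1 | 95.0 | 95.1 | 95.1 |

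At 1% v 2%, Wald covers 73.8% (n=45) and 77.3% (n=50). At 2% v 4% it covers 89.5% and 86.4%, so more subjects do not always help: the counts are discrete. With both rates between 10% and 50%, mean Wald coverage is 94.4% and the minimum 93.7% (n=45) or 93.8% (n=50).

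**Empty cells.** With 0 v 0, Wald gives [0, 0].
- Newcombe's half-width is the Wilson upper limit, (3.84/n) / (1 + 3.84/n): 7.9 points at n=45 and 7.1 at n=50.
- Miettinen-Nurminen gives 7.9 and 7.2.
- The chance of 0 v 0 is (1−p1)ⁿ(1−p2)ⁿ. At n=50 with equal rates this is 37% at 1%, 13% at 2%, 0.6% at 5% and under 0.01% at 10%.
- At 2% v 5% and n=45 it is 4.0%, and all of that counts as non-coverage.

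**One empty arm.** The interval does not collapse.
- 0/45 v 3/45: Wald −14.0 to +0.6 points, Newcombe −17.9 to +2.3.
- 0/45 v 4/45: Wald is −8.9 ± 1.96 × √(0.0889 × 0.9111/45) = −8.9 ± 8.3, or −17.2 to −0.6, which excludes zero. Newcombe's upper limit is −0.0889 + √(0.0787² + (0.0889 − 0.0351)²) = +0.006, which includes it.
- The Miettinen-Nurminen statistic at zero difference is −0.0889 / √(0.0444 × 0.9556 × (2/45) × (90/89)) = −2.03, so that interval also excludes zero.

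**T0+12 hours.** The number attending is not given. Over an assumed range, Wald coverage at 2% v 5% and at 5% v 10% is 84.8% and 93.0% (30 per arm), 80.4% and 91.1% (25), and 75.6% and 85.8% (20). Newcombe covers at least 96% in all of these.

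**Plausible rates (assumed figures).** Take mean baseline 25 mmHg, SD 3.0 and whole-mmHg readings, so a responder reads below 18.5. Mean falls of 2, 3, 4, 5 and 6 mmHg give rates of 7%, 12%, 20%, 31% and 43%. Wald covers 94.0-94.5% at adjacent pairs. Varying the baseline over 24-26 and the SD over 3.0-3.6 moves the rates between 3% and 57%.

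**The case against.** The strongest reply is that this is a textbook preference on a descriptive summary, and much of it stands. SAP 4.3 confines the fixed sequence to the primary endpoint, so no decision rule uses these intervals. Each arm's exact interval is printed as well, so an empty cell still shows its uncertainty. At ordinary response rates the shortfall is about half a point. The remedy is not exact either: Newcombe over-covers at very low rates, and Miettinen-Nurminen covers 93.7% at 2% v 10% with 50 per arm, against Wald's 93.3%.

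Three stronger readings are tempting, and the documents do not support them.
- A reader might infer that Wald is too narrow whenever rates are low. At equal low rates it is conservative or about nominal.
- A reader might infer that one empty arm collapses the interval. Both arms must be at 0 (or both at 100%).
- A reader might infer from the 23 mmHg entry floor that responders will be scarce. Inclusion criterion 3 (Protocol 4.1) applies that floor only to the study eye at T0 on Day 1. It sets none at later hours or for the fellow eye, and mean diurnal IOP excludes Pre-T0. The one cell where the floor guarantees 0 v 0 among eligible subjects is Day 1 Pre-T0, before dosing, where no treatment effect is estimated.

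What survives is narrower: the stated method fails in identifiable tables, the SAP has no fallback for them, and a better method needs no extra data.

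**Conclusion.** The point holds as a minor, cheap improvement. At 45-50 per arm, the loss of coverage is material only when the true rates differ and at least one is below about 5% (roughly 4 to 6 points short at 2% v 5%, more at lower rates), or when neither arm has a responder. Elsewhere Wald is adequate. Smaller denominators at the optional T0+12 hour time point would enlarge the problem, but by how much depends on attendance figures that the documents do not give.

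The coverage figures are exact for two independent binomials of equal size. Whether such cells will occur on treatment is unknown, because it depends on responder rates that neither document states. A reader might infer that the trial's non-inferiority conclusion is exposed; it is not, since the endpoint lies outside the testing hierarchy.

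**What to change.** In SAP 4.11.2, replace the Wald method with the Miettinen-Nurminen score interval for every difference in proportions: IOP at each visit and time point, and both mean diurnal versions. The fellow-eye repeat in SAP 4.11.3 should follow the same method. Newcombe's interval is an acceptable alternative if a conservative method is preferred. Name one of the two in advance, because they can disagree in borderline tables such as 0/45 v 4/45.

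The cost is a changed option in the analysis program and one sentence in a SAP amendment, which the SAP introduction allows before database lock. No subjects, data or endpoints change. The downside is somewhat wider intervals in sparse cells and some over-coverage at very low rates, more so with Newcombe. Settling this now also avoids a post hoc change of method if a zero-width interval appears.
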